#### **Statistical Analysis Plan Table**

Evaluation	Change from baseline	Notes/Interpretation
Investigator	The mean score (0-4) will	Significantly greater than 0
Quartile	be compared to the	indicates improvement.
Improvement	constant 0, using Wilcoxon	
Score	signed rank test	
SAEs	NA	Zero or low number of SAEs is
		favorable
Tolerability	NA	Lower score indicates better
parameters		tolerability
VAS	NA	Lower score indicates better
		tolerability
Biopsy parameters	NA	Descriptive statistics only
Individual	NA	A binomial test (sign test) P value
response data		will be provided. A higher
(GAIS and		percentage of combined favorable
satisfaction)		responses with a significant P
		value indicates positive subject
		perceptions of the test material.
Blinded	The mean score (0-4) will	Significantly greater than 0 indicates
Investigators	be compared to the	improvement.
	constant 0, using Wilcoxson	
	signed rank test	

All statistical tests will be 2-sided at significance level alpha=0.05 unless specified otherwise. *P* values will be reported to 3 decimal places (0.000).

No multiple testing corrections will be considered in the study. Statistical analyses are performed using SAS software version 9.4 (SAS Statistical Institute). The statistical results will be sent to the Sponsor along with raw data in a Microsoft Excel document at completion of the study.

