### 4.2.3 Safety Endpoints

Serious Adverse Events (SAEs) related and unrelated to the treatment procedure or to the CLEAR + BRILLIANT TOUCH® diode laser.

The severity of post-treatment skin responses:

- Immediate post-treatment erythema and edema (Visits: 1 and or 2 if screening and treatment on same day, Visits 3, 4 and 5)
- Prolonged post-treatment erythema, edema, dryness/flakiness, hypopigmentation, hyperpigmentation, blistering, scarring. (Visits 6 & 7)

The evaluation of pain and discomfort immediately after the treatment (within 60 minutes) as reported by the subject on a visual analog scale (VAS).

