### 5.2 Number of Participants

Up to 30 subjects who meet all study/exclusion criteria will be considered for entry.

Application of the inclusion and exclusion criteria in the following sections will result in the selection of an investigational population which is approximately representative of the intended target population.

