#### 10. STATISTICS

### 10.1 Statistical Analysis Populations and Demographics

The intent-to-treat (ITT) population will be the primary population for all statistical analyses. The ITT population will include all subjects who received treatment, participated in at least 1 post-baseline evaluation, and were not otherwise disqualified.

Subjects may be removed from the analysis in the case of an AE, SAE, noncompliance, or Investigator decision. The reason for any subject(s) excluded from an analysis population will be documented in a note to file and included in the study report.

Demographic data and baseline characteristics, including age, gender, ethnicity, Fitzpatrick skin type, Glogau rating, and Fitzpatrick wrinkle & elastosis scale rating, will be summarized according to the analysis population for all subjects. For continuous variables, descriptive statistics including number of subjects (N), mean, median, standard deviation (SD), minimum (MIN) and maximum (MAX) values will be presented. For categorical variables, the count and percentage of each category will be provided. The denominator for all percentages will be the number of subjects with non-missing data at the given visit for each respective study treatment, unless otherwise indicated.

The sample size determination of this study is based on the Sponsor's recommendations to quantify the effectiveness and safety of the CLEAR + BRILLIANT TOUCH® diode laser 1440-nm and 1927-nm Laser in the context of this study. Power calculations were performed based on estimates for expected mean change and variance in overall appearance at 3 months as rated by the Investigator using the Quartile Improvement Scale from study 12-133-CBP-F ('Evaluation of the skin after treatment with the Clear + Brilliant 1927-nm wavelength laser by means of the VISIA-CA Imaging System'). The power calculations demonstrated a sample size of 25 has greater than 95% power to reject the null hypothesis (change from baseline=0) for the primary efficacy endpoint. Thus, up to 30 subjects will be enrolled to account for potential drop-out.

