### 10.2 Statistical Analysis Plan (SAP)

#### 10.2.1 Descriptive Statistical Summary

A descriptive statistical summary will be provided for Investigator Quartile Improvement Score (IQIS, 0-4), tolerability parameters, VAS scores, and biopsy parameters. The descriptive statistical summary includes the N, mean, median, SD, MIN, and MAX of scores/values at all applicable time points.

Counts and percentages will be provided for Investigator Quartile Improvement Score (rating), SAE parameters, tolerability parameters, VAS (in category), and individual response data (GAIS and subject satisfaction).

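### SAEs are to be reported as bare counts and percentages read as favorable when zero or low, yet zero events in at most 30 subjects leaves a two-sided 95% exact upper limit of 11.6%

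*Combined protocol and SAP*

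**What the plan says.** Section 3 gives effectiveness and safety equal place in the single objective. Section 4.2.3 lists three kinds of safety endpoint: SAEs, graded skin responses and pain on the VAS. The first reads "Serious Adverse Events (SAEs) related and unrelated to the treatment procedure or to the CLEAR + BRILLIANT TOUCH® diode laser".

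Section 10.2.1 sets the summary: "Counts and percentages will be provided for Investigator Quartile Improvement Score (rating), SAE parameters, tolerability parameters", together with the VAS in categories and the subject-reported responses. For scores, "The descriptive statistical summary includes the N, mean, median, SD, MIN, and MAX of scores/values at all applicable time points". In the Statistical Analysis Plan Table of section 10.2.2, the SAE row has NA under change from baseline, and its interpretation column says "Zero or low number of SAEs is" favorable. No value is attached to low. Section 10 plans no confidence interval for any endpoint, and none appears elsewhere in the supplied text.

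On numbers, section 5.2 says "Up to 30 subjects who meet all study/exclusion criteria will be considered for entry", and section 5.9.1 rules out replacing withdrawn subjects. The sample size rests on effectiveness only: "The power calculations demonstrated a sample size of 25 has greater than 95% power to reject the null hypothesis".

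Section 10.1 makes the ITT population primary for all statistical analyses. It consists of treated subjects with at least one post-baseline evaluation who were not otherwise disqualified. The same section lets subjects be taken out of the analysis because of an adverse event, serious or not, with the reason documented in a note to file and in the study report.

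**The concern.** A single-arm study of this size produces estimates, and an estimate without an interval does not show how much it leaves open. The likeliest SAE result is none or very few. The plan attaches one word to that result, favorable, and nothing that says which event rates the data exclude. Section 9.2 describes complications as having very low incidence or as very rare, and a bare zero in 30 subjects cannot test statements of that kind.

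The denominator adds to the problem. If a subject can leave the analysis because of the event being counted, the reported percentage is no longer the rate among those treated. At stake is how strongly the study can speak on half of its objective. The same lack of intervals affects the effectiveness percentages, where the Wilcoxon and sign tests give P values but no precision.

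**Working it through.** **Inputs.** Maximum n = 30 (section 5.2). n = 25 is the figure behind the power statement (section 10.1). Two-sided alpha = 0.05 comes from the text under the Statistical Analysis Plan Table: "All statistical tests will be 2-sided at significance level alpha=0.05 unless specified otherwise". The documents state no confidence level, so carrying that alpha over to a 95% interval is an assumption. Zero observed SAEs is a scenario; the documents give no expected SAE rate.

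**The plan's own figure.** The only sample-size figure is power above 95% at n = 25 for the effectiveness endpoint. It cannot be reproduced, because the mean change and variance from the earlier study are not given. By normal approximation it needs a standardized mean change of at least (1.960 + 1.645)/√25 = 0.72; a one-sample t calculation gives about 0.76. Neither bears on the precision of the safety results, for which the plan gives no figure.

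**Upper limit for zero events.** The exact (Clopper-Pearson) two-sided 95% limit is 1 − 0.025^(1/n); the one-sided 95% limit is 1 − 0.05^(1/n).

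| n | Two-sided 95% | One-sided 95% |
|---|---|---|
| 30 | 1 − 0.025^(1/30) = 11.6% | 1 − 0.05^(1/30) = 9.5% |
| 25 | 1 − 0.025^(1/25) = 13.7% | 1 − 0.05^(1/25) = 11.3% |

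Other methods at n = 30 give similar limits: 3/30 = 10.0% by the rule of three and 11.4% by Wilson. Because 30 is a ceiling, 11.6% is the best case for the two-sided exact limit.

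**Small non-zero counts at n = 30.** One event is 3.3%, with exact 95% interval 0.08% to 17.2%. Two events are 6.7%, with interval 0.8% to 22.1%.

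**How often zero would be seen.** The chance of no event in 30 is (1 − p)^30. The rates are illustrative assumptions.
- p = 2%: 0.98^30 = 54.5%
- p = 5%: 0.95^30 = 21.5%, so at least one SAE would appear 78.5% of the time

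**Effect of a removal.** Suppose one of 30 treated subjects has an SAE and is taken out of the analysis because of it. The result changes from 1/30 (3.3%, upper limit 17.2%) to 0/29 (0%, upper limit 1 − 0.025^(1/29) = 11.9%). An interval alone does not repair this; the denominator has to be fixed as well.

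**Effectiveness, for scale.** A hypothetical 25 of 30 improved is 83%, with exact 95% interval 65% to 94%.

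**The case against.** The strongest reply is that this is a small descriptive study of an FDA-cleared system, sized for effectiveness, in which the table note only states a direction. The tolerability and VAS rows are worded in the same way, with lower meaning better. That stands. A reader might infer that the note is a pass/fail rule returning favorable by default, but the documents set no safety success criterion.

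A reader might also infer that zero events would be expected even at an unacceptable rate. The documents do not support that either. They name no unacceptable rate, and at an assumed 5% a zero is the less likely outcome.

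A third tempting reading is that SAEs could be concealed. Section 8.1.1 requires every SAE to be reported to the sponsor, section 8.2 requires adverse events to be recorded through the last follow-up visit, and section 10.1 requires exclusions to be explained in the study report. The removal clause is permissive and does not single out safety. What it leaves open is the analysed count and its denominator.

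It can be said that readers could compute an interval from the printed counts. They could if the denominator were the treated subjects. Section 10.1 instead uses subjects with non-missing data at the visit, within a population open to removals. Section 8.5, under which a related SAE may lead to a recommendation to terminate or modify the study, governs conduct and does not estimate a rate.

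**Conclusion.** The point holds as a gap in reporting and precision; it is not an arithmetic error in the plan. SAE counts and percentages are planned, but nothing shows what they exclude. With 30 subjects and no SAE, the data would exclude rates above 11.6% (two-sided 95% exact), or above 13.7% with 25. The choice of interval method moves the n = 30 limit only between 9.5% and 11.6%, so the conclusion does not depend on it. Whether a limit of that size is acceptable is a judgment that the documents do not make.

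The ITT definition and the removal clause make the matter somewhat worse, because an analysed zero could differ from the number of events among treated subjects. No planned test or endpoint changes, but the safety conclusion should be limited to what the interval supports.

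**What to change.** 1. Replace the SAE note in the Statistical Analysis Plan Table with: *Number and percent of all treated subjects with at least one SAE and with at least one related SAE, with two-sided exact (Clopper-Pearson) 95% CI; zero counts are reported with their upper limit.*
2. State in section 10.1 that safety analyses include every treated subject and that removals for an AE or SAE do not apply to them.
3. For skin responses, which section 8.1 scores from 0 to 3, report the distribution of scores and give an exact 95% CI for the proportion with any response (score of at least 1).
4. Add 95% CIs for the percentages from the Investigator Quartile Improvement Score, GAIS and satisfaction, and for the mean Investigator Quartile Improvement Score.

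The cost is SAP wording and a few lines of SAS, with no new data, visits or subjects. The downside for the sponsor is a less favorable safety statement.

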10.2.3 Minimization of Bias and Potential Confounding Factors
Blinded investigator photo evaluation is intended to minimize bias.

#### 11. SOURCE DOCUMENTS AND ACCESS TO DATA/DOCUMENTS

The PI shall supply the study monitor or IRB on request with any required background data from the study documentation or clinic records.

This clinical investigation will permit the investigator to proceed with "data entry" directly onto the case report forms (CRFs). In this case, the CRFs will also serve as the source record for each participating subject. A copy of the CRFs will be collected by SGS Stephen's Inc. for data analysis.

### 12. QUALITY ASSURANCE AND QUALITY CONTROLS

Each investigational site will undergo a detailed training that highlights the key tenets for maintaining quality management. The investigational sites will be instructed regarding protocol compliance, use of CRFs, and proper treatment administration. The investigator must assure that subject confidentiality will be maintained and that participant identities shall be protected from unauthorized parties.

#### 12.1 Study Monitoring

The Sponsor and its representatives must be allowed to visit the study site location to assess the data, quality, and study integrity.

Prior to the start of the study, member(s) of the Sponsor (or designees) will review the protocol, CRF, regulatory obligations, and other material or equipment relevant to the conduct of the study with the Investigator and relevant study site personnel.

Monitoring visits and telephone consultations will occur as necessary, as per the monitoring plan, during the course of the investigation. During the course of the study, all data will be 100% source document-verified by the monitors when possible. All subject source documents must be made available to the monitors.

### 13. ETHICS OF HUMAN SUBJECTS AND ADMINISTRATIVE ISSUES

### 13.1 Ethical Standard

The investigator will ensure that this study is conducted in full conformity with the principles set forth in the Declaration of Helsinki, EN ISO 14155:2020 Clinical Investigation of Medical Devices for Human Subjects – Good Clinical Practices, 21 CFR 803 Medical Device Reporting, International Conference of Harmonization Good Clinical Practice Guidelines and all other applicable regulatory requirements and standards. The study will also be carried out in keeping with applicable regulations and guidelines governing clinical study conduct and local legal requirements.

Each investigator confirms this by signing this study protocol.

#### 13.2 Institutional Review Board

Before commencing with and enrolling volunteers for this proposed study, the appropriate documents (including the Protocol, Investigator's Brochure, Informed Consent Form, information sheets, CRF's and advertisements) will be submitted to the IRB. The investigator will be responsible for obtaining IRB approval for the study. Protocol deviations will also be reported to the IRB according to the policy of the board. Protocol amendments will be reviewed and approved by the IRB prior to implementation of any changes made to the study design in the amendment.

The investigators will inform the IRB:

- All subsequent protocol amendments, informed consent changes or revisions of other documents originally submitted for review
- Serious and/or unexpected adverse events occurring during the study, where required
- New information that may affect adversely the safety of the participants or the conduct of the study
- An annual update and/or request for re-approval, where required barring unforeseen circumstances, this study is anticipated to be completed within 9-10 months.
- When the study has been completed.

#### 13.3 Informed Consent Process

Informed consent is a process that is initiated prior to the individual's agreeing to participate in the study and continues throughout the individual's study participation. Extensive discussion of risks and possible benefits of this therapy will be provided to the subjects and their families. Consent forms describing in detail the study interventions/products, study procedures, and risks are given to the subject and written documentation of informed consent is required prior to starting intervention/administering study product. Consent forms will be IRB-approved, and the subject will be asked to read and review the document. Upon reviewing the document, the investigator will explain the research study to the subject and answer any questions that may arise. The subject will sign the informed consent document (ICD) prior to any procedures being done specifically for the study. The subjects should

Page 36 of 49

have the opportunity to discuss the study with their surrogates or think about it prior to agreeing to participate. The subjects may withdraw consent at any time throughout the course of the trial. A copy of the ICD will be given to the subjects for their records. The rights and welfare of the subjects will be protected by emphasizing to them that the quality of their medical care will not be adversely affected if they decline to participate in this study. The subject will be asked to sign and date prior to participating in the study.

The informed consent will require a signature. Additionally, subjects will be provided with a copy of consent form to disseminate to all pertinent parties for proper discussion in order to make an informed decision concerning their participation. Should a protocol addendum be made, the subject consent form may be revised to reflect the changes of the protocol. If the consent form is revised, it is the responsibility of the investigator to ensure that an amended consent is reviewed and approved by the IRB. The approved amended consent form should be signed by all subjects subsequently entered in the study and by those subjects currently in the study, if required by the IRB. The terms of the consent and when it was obtained must also be documented in the CRF.

#### 13.4 Participant and Data Confidentiality

Subject confidentiality is strictly held in trust by the participating investigators, their staff, and the sponsor(s) and their agents. This confidentiality is extended to cover all recorded information during the clinical study. The clinical investigation will be registered in a publicly available database. In addition, the results of the study will be published in a publicly available database.

The study protocol, documentation, data, and all other information generated will be held in strict confidence. No information concerning the study, or the data, will be released to any unauthorized third party without prior written approval of the sponsor.

The study monitors or other authorized representatives of the sponsor may inspect all documents and records required to be maintained by the investigator, including but not limited to, medical records (office, clinic, or hospital) and pharmacy records for the subjects in this study.

Subjects' identities will be kept confidential by assigning each subject a subject ID upon acceptance into the study. The subject ID will comprise the site ID and a three-digit number that will be based upon the subject's order of entry into the study. The study Sponsor will not receive any additional identifying information about a subject and will therefore have no way of linking a subject ID to a subject and his or her results.

13.4.1 Research Use of Stored Human Samples, Specimens or Data ProPath may dispose of biohazard human biopsy samples per local and federal guidelines after processing of samples.

#### 13.5 Financial Disclosure

Financial disclosures will be obtained from all investigators in order to document any potential conflicts of interest. An original Financial Disclosure Form (FDF) must be completed, signed and dated by the principal investigator (PI) and any sub-investigators. All FDFs will be collected by the Sponsor or its designee and filed in the study Trial Master File. A copy of all FDFs will be retained in the Investigator Site Binder.

#### 13.6 Finance

The study is financed by the Sponsor. The Sponsor carries insurance that covers clinical trials, which is filed under the company's Master Policy for clinical trials conducted within the U.S.

#### 14. DATA HANDLING AND RECORD KEEPING

#### 14.1 Data Collection and Management

Data collection is the responsibility of the study staff at the site under the supervision of the site principal investigator. During this study the investigator must maintain complete and accurate documentation for the study.

Data management and oversight is the responsibility of the Sponsor and SGS Stephens Inc. Responsibilities include but are not limited to the following

- Clinical strategy and oversight
- Clinical study operations
- File management and study documentation
- Site initiation visit and study closeout visits
- Clinical quality assurance
- Statistical support and programming
- Data management including database development and programming and electronic data capture programming training and management

Additionally, management and oversight of photographic imaging is the responsibility of the Sponsor and SGS Stephens Inc (Clinical Research Organization).

Responsibilities may be delegated to applicable vendors.

Data will be recorded on case report forms (CRFs). A CRF is required and should be completed for each included subject.

A single-entry method will be used to enter the data captured on paper records into an electronic data capture (EDC) system. Numerical data described in Section 7 will be recorded using the SGS Stephens EDC system, which documents the identity of the evaluator/technician as well as the time and date of all entries, or all corrected entries. The

SGS Stephens EDC is a computerized system designed for the collection of clinical data in electronic format. The 3 major aspects of EDC are a graphical user interface for data entry, a validation component to check for user data, and a reporting tool for analysis of the collected data. The entries will be compared to the paper CRFs with 100% source document verification by the monitors when possible to ensure that the data is transferred accurately from the paper records to the electronic database, and any missing data and/or inconsistencies will be identified and corrected.

It is the investigator's responsibility to ensure completion, review and approve all CRFs. CRFs must be signed by the investigator or authorized staff member. These signatures serve to attest that the information contained on the CRFs are true. At all times, the investigator has final personal responsibility for the accuracy and authenticity of all clinical and laboratory data entered on the CRFs.

Photographic images will be captured utilizing the Canfield Scientific, Inc. VISIA CA Imaging system.

